# Section F: Design/Procedure

## F1. Design

Select one category that most adequately describes your research:

c) Pilot

Discuss the research design including but not limited to such issues as: probability of group assignment, potential for subject to be randomized to placebo group, use of control subjects, etc.

Thirty four (n=50) patients with diabetes (age 18 years or older) with non-infected deep wounds (grades 2 in the Wagner Ulcer classification) will be randomized into two groups, 17 subjects per group each. The group one will be treated by Meshed DermaCELL and group two will be treated by Meshed Integra template.

The primary outcomes are time to granulation, successful granulation at 8 weeks, and number of failures (e.g. amputation, infection, rejection, re-application) within 8 weeks. Secondary outcomes include time to apply, weekly speed of wound healing after successful granulation and transition to standard wound therapy, success of wound healing at 12 weeks and @16 weeks, cost of wound treatment upto 16weeks (based on patient electronic record), tissue biomechanics after wound healing (e.g. presence of scarring or tissue biomechanics properties leading to increase in shear or pressure post healing), change in skin perfusion (assessed with SPP), change in thermography response, recurrence of ulcers up to 6 months post healing, and other patient centered outcomes including perception of pain, physiological stress response as surrogate of pain (e.g. heart rate variability during dressing change), sleep quality (assessed by PSQI and sensor-based sleep quality index), wound smelling (assessed by Likert scale), and patient perception of benefit (assessed by technology acceptance model, TAM based on perception of benefit and attribute of benefits).

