#### F2. Procedure

\*\* Reliance protocol \*\* There are a total of 17 study visits.

Medical History: The presence of diabetes will be determined based on American Diabetes Association criteria. This will include: duration and type of diabetes, type of diabetes medication (insulin, oral, combination therapy, diet), previous history of foot ulcers, amputation (toe, foot), lower extremity bypass, lower extremity angioplasty, Coronary artery bypass surgery, cardiac angioplasty, arthritis, liver disease, osteoporosis, malignancy, and bone tumors. We will use the Kaplan co-morbidity index to record disease severity.

Social and Economic Factors: We will evaluate the following factors: marital status, years of education, type of work, tobacco history (pack years, current smoker, current use of chewing tobacco, previous smoker, no tobacco history), drug history (current, previous history, no drug history), and alcohol history. Also we will collect cost information for the subject's treatment up to 6 months after the subject enrolls in the study.

Questionnaires: Quality of Life, Frailty Status, Sleep Quality, Cognitive Status and Device Acceptability: To evaluate functional status we will use well-accepted questionnaires, SF-12 for Quality of Life, Sleep Quality questionnaire (PSQI), MOCA and TSFI for frailty status. In addition, at each visit, we will interview the subject about their concern with their wound and product (e.g. wound drainage, smell, pain, etc.), use of any medications for pain or sleeping, the cost of transport to the clinic, any adverse events (e.g. infection, need to visit a specialist, etc), etc. To see the timeline for each questionnaire, please refer the table included in the ICF attached.

Pain Intensity Assessment (VAS): Researchers will provide a numerical pain scale where subject will report their pain intensity. Researchers will document pain level.

Adverse Event Reporting: Researchers will document and report any study/non study related incident as per institution regulations.

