Granulation Assessment: The physician will be looking at how the wound heals. Specifically, they will look at the reddish tissue developing on the wound. A digital photograph will be taken and comments made by the physician will be recorded.

Wound Care: The physician will schedule regular visits after the surgery to provide care to the wound as according to standard of care

Dressing Change: Medical and/or clinical staff will change the subject's dressing weekly or as needed.

Peripheral Neuropathy: We will use Vibration Perception Threshold (VPT) Testing to quantify neuropathy severity. VPT will be evaluated at the distal great toe and 5th metatarsal head using a Biothesiometer.

Upper Extremity Assessment: Investigators will measure the subject's arm motion using wearable sensors (LegSys). One sensor will be placed around the wrist and elbow. While being at a comfortable position, they will be asked to flex and extend their arm for 20 s at a fast speed. We will ask to repeat this task but counting backwards (dual task).

Optional Assessments ¿ These may occur at any visit. However, they do not need to be performed.

Physical Exam: The researchers will place 5 sensors named Legsys and Balanses (one on lower back, 2 on each upper thigh, and 2 on each shin) attached with elastic straps to test balance and record your walking patterns. Researchers will ensure that the straps are not too tight to avoid poor circulation

Physical activity: The researchers will provide you with a small sensor (Pamsys) that will be measuring physical activity for 48 hrs. It will record number of steps taken, duration of sitting, standing, walking, and lying. At the end of the visit, the subject will be given the sensor, which will be worn, around the neck. Researchers will provide a pre-paid envelope where they may place the device and send it back to the investigating team after 48 hrs

Heart Rate Monitoring: A comfortable chest worn sensor (Zephyr BioHarness, Medtronic or BioStamp RC, MC10) will be used to measure physiological signs such as heart rate, skin temperature, and physical activity. This device will be comfortable placed on the chest attached either with 2 electrodes or with elastic straps if the subject has sensitive skin. Researchers will attach this device on the subject for the duration of the visit or during 24 hours

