The description of every visit is below. Screening/Baseline Visit \*duration of visit 90 minutes This visit will take place at Baylor St. Lukes Medical Center during your surgery day. The researchers will perform as described above: Medical History, Questionnaires (Pain, Social Factors, and Quality of Life, Sleep Quality, Cognitive Assessment, Frailty), Matrix application, Upper Extremity Test, Peripheral Neuropathy, Thermal Image, Vascular Assessment, Wound Assessment, Wifi Wound Classification, and Wound photo.

Visit 1, One Week Later \*duration 50 minutes This visit will take place at Baylor Clinic for a regular follow up appointment. The researchers will perform as described above: Pain Questionnaire, Adverse Event Reporting, Dressing Change, Wound Photo, and Wound Care.

Visit 2, Two Weeks Later \*duration 70 min This visit will take place at Baylor Clinic for a regular follow up appointment. The researchers will perform as described above: Adverse Event Reporting, Wound Assessment, Thermal Image, Dressing Change, Wound Photo, and Wound Care.

Visit 3, Three Weeks Later \*duration 50 min This visit will take place at Baylor Clinic for a regular follow up appointment. The researchers will perform as described above: Adverse Event Reporting, Dressing Change, Wound Photo, and Wound Care.

Visit 4, Four Weeks Later \*duration 70 min This visit will take place at Baylor Clinic for a regular follow up appointment.

The researchers will perform as described above: Pain Questionnaire, Adverse Event Reporting, Sleep Quality Questionnaire, Wound Assessment, Dressing Change, Wound Photo, Thermal Image, and Wound Care.

Visit 5, Five Weeks Later \*duration 70 min This visit will take place at Baylor Clinic for a regular follow up appointment. The researchers will perform as described above: Adverse Event Reporting, Dressing Change, Wound Photo, Granulation Assessment, and Wound Care.

Visit 6, Six Weeks Later \*duration 70 min This visit will take place at Baylor Clinic for a regular follow up appointment. The researchers will perform as described above: Adverse Event Reporting, Dressing Change, Thermal Image, Wound Photo, Granulation Assessment, and Wound Care.

Visit 7, Seven Weeks Later \*duration 70 min This visit will take place at Baylor Clinic for a regular follow up appointment. The researchers will perform as described above: Adverse Event Reporting, Dressing Change, Wound Photo, Granulation Assessment, and Wound Care.

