## G2. Data Analysis

Provide a description of your plan for data analysis. State the types of comparisons you plan (e.g. comparison of means, comparison of proportions, regressions, analysis of variance). Which is the PRIMARY comparison/analysis? How will the analyses proposed relate to the primary purposes of your study?

The primary outcomes are time to granulation, successful granulation at 8 weeks, and number of failures (e.g. amputation, infection, rejection, re-application) within 8 weeks. Mixed models accommodate the longitudinal design; allow for testing differences between groups in patterns over time as well as at specific time points; are consistent with an intention to treat analysis (9), and are valid for data which are missing completely at random or at random (10). Number of failures as well as number of recurrence of ulcers over the 6 month follow-up will be modelled with a generalized linear model using an appropriate count outcome (Poisson, zero-inflated Poisson, negative binomial for overdispersion). Rate ratios comparing intervention arms will be estimated from this model. Appropriate mixed models (linear or generalized linear, for noncontinuous outcomes or logistic regression for binary data) will be used to test the intervention effect for each of the secondary outcomes (e.g. tissue biomechanics, mobility, patient centered outcomes, recurrence of ulcers, etc). A Kaplan-Meier survivorship analysis will be used for estimating time to event for none successful healing probability over time by treatment and the p-value will be calculated using the Log-rank (Mantel-Cox) test. Hazard ratios will be used to indicate the probability of closure at any given point in time for Derma-Cell v. Integra treatment. Univariate logistic regression analyses will be performed to delineate predictive factors of successful granulation at 8 weeks, successful wound healing at 12 weeks, and successful wound healing at 16 weeks. Results will be controlled for potential confounding variables including age, sex, BMI, HbA1c, neuropathy severity, vascular status, frailty, mobility status, and initial wound size. The p-values for weekly % wound area and % wound area reduction through 16 weeks will be calculated using t tests. All p-values, for both the categorical and continuous data, will be calculated using a two-sided alpha of 0.05.

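### Nine adjustment covariates are listed for 34 or 50 patients with no model named; if all nine enter a logistic treatment comparison fitted by maximum likelihood, the odds ratio is unstable, and too far from 1 when a true effect exists

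*Combined protocol and SAP*

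**What the plan says.** The adjustment rule is one sentence in section G2: "Results will be controlled for potential confounding variables including age, sex, BMI, HbA1c, neuropathy severity, vascular status, frailty, mobility status, and initial wound size". The word before the list makes nine a minimum. No model is attached, and there is no rule for selecting, reducing or penalising covariates or for handling missing ones.

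The preceding sentence concerns predictors, not arms: "Univariate logistic regression analyses will be performed to delineate predictive factors of successful granulation at 8 weeks", and likewise for healing at the two later time points. Earlier in G2, logistic regression is also named for comparing the arms: "logistic regression for binary data) will be used to test the intervention effect for each of the secondary outcomes". Section F1 lists "success of wound healing at 12 weeks and @16 weeks" among the secondary outcomes. For successful granulation at week 8, a primary outcome, G2 names no model that compares the arms.

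F1 gives the sample size as thirty-four in words, 50 in figures and 17 per group; G1 gives 50. G1 bases 17 per group on application time alone.

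Mobility status is not defined. The sensor tests of gait, balance and activity in section F2 are optional: "These may occur at any visit. However, they do not need to be performed". G2 also treats mobility as an outcome: "test the intervention effect for each of the secondary outcomes (e.g. tissue biomechanics, mobility, patient centered outcomes".

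**The concern.** Read as written, the rule covers any result, including the logistic comparison of arms for healing at weeks 12 and 16, and week-8 granulation if it is analysed the same way. That means treatment plus nine covariates, ten slopes, in a very small trial. Maximum-likelihood logistic regression behaves poorly there: the estimate may not exist because of separation, it scatters widely, and a true effect is exaggerated.

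The reported adjusted odds ratio and its interval are at stake. G1 says that a further trial may follow if trends are seen. Because the text allows anything from no covariates to all nine, the choice could also be made after the results are known.

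Mobility status adds a separate difficulty. If it comes from the optional sensor tests, it may be missing or recorded after treatment, and a complete-case analysis would then shrink the sample further.

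**Working it through.** **The plan's own figure.** G1 assumes 3±2 against 5±2 minutes, so d = 2/2 = 1, with two-sided alpha 5% and power 80%. The exact noncentral t solution is 16.71, so 17 per group, with power 80.7%. The figure reproduces. It concerns an unadjusted comparison of means and says nothing about binary outcomes or covariates.

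**Events per slope.** Slopes = 1 + 9 = 10. Events per slope = N × min(p, 1 − p)/10.
- At most (p = 0.5): 17/10 = 1.7 at N=34; 25/10 = 2.5 at N=50.
- At 70% success: 10.2/10 = 1.0; 15/10 = 1.5.

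**Simulation inputs.** From the documents: N of 34 or 50, 1:1 allocation, nine covariates, two-sided 0.05. Assumed, because the documents give no rates or covariate effects: overall success 60/70/80%; wound-size log-odds effect 0.5 per SD; the other eight covariates inert and all covariates independent; treatment log odds ratio 0 or 1.0 (odds ratio 2.7). Separated fits are left out of the maximum-likelihood (ML) medians and shares.

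**True odds ratio 2.7, nine covariates, ML.** The median estimate is about 4–5 at N=34 and 3.6–3.9 at N=50; independent repeats ranged over 3.8–5.2 and 3.6–4.1. Firth with all nine gives 2.5–2.8.

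A second design (comparator success 0.5 or 0.7, true odds ratio 3) isolates the covariate count:
- Nine covariates, ML: median 5.0–5.4 (N=34) and 4.1–4.7 (N=50).
- Two inert covariates, ML: 3.0–3.4 and 3.2–3.3.
- Nine inert covariates, Firth, success 0.5: 2.97 and 3.02.

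The inflation is therefore small-sample bias and not non-collapsibility: it appears with inert covariates and Firth removes it.

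**No true effect, nine covariates, ML.** The median odds ratio is 0.90–1.03. Separation occurs in about 5–37% of fits at N=34 and 0–5% at N=50. Wald type I error is 4.3/2.5/1.2% at N=34 and 6/6/3.5% at N=50.

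Share of fits with an odds ratio at least threefold from 1, N=50, no effect (500 runs, so the standard error at 25% is √(0.25 × 0.75/500) = 1.9 points):

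| Model | 60% | 70% | 80% |
|---|---|---|---|
| Nine covariates, ML | 25 | 29 | 40 |
| Two covariates, ML | 11 | 14 | 20 |
| Nine covariates, Firth | 11 | 15 | 19 |
| Unadjusted, ML | 7 | 11 | 14 |

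The excess of nine-covariate ML over the unadjusted model is 18/18/26 points. Cutting to two covariates leaves 4/3/6; Firth with all nine leaves 4/4/5. Each change alone removes about 77–83% of the excess. A separate run gave 24/26/39, 11/13/20 and 14/14/20 for the first three rows; 24/11 = 2.2, 26/13 = 2.0 and 39/20 = 1.95, so roughly double.

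At N=34 the nine-covariate ML share is 44/49/55%. Even the unadjusted odds ratio is threefold off in about 13–24% of fits.

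**Sensitivity.** If each of the other eight covariates has an effect of 0.3 per SD, no-effect separation is 12/23/49% (N=34) and 0.3/0.9/12% (N=50), and the nine-covariate median for a true 2.7 is 4.4–5.1 and 4.0–4.3.

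**Linear models.** These stay unbiased. Nine inert covariates raise the expected variance of the treatment estimate by (N − 3)/(N − 12): 31/22 = 1.41 or 47/38 = 1.24. They are not part of this point.

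**The case against.** The strongest reply is that the plan never commits to this model. The covariate sentence follows the predictor analysis and may govern only that; no covariate set is attached to the logistic comparison of arms. This stands, and it is why the point is conditional. It does not settle the text: a one-variable model cannot at the same time be controlled for nine variables, and the sentence is not restricted to predictors.

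Healing also has its own comparison in G2, by Kaplan–Meier, log-rank and hazard ratio. That is so, but the logistic sentence covers every secondary outcome, and F1 lists healing at two fixed weeks.

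Section D assumes that wound outcomes are comparable, so the inflation might never arise. That is fair: with no effect only the scatter and the separation remain. The study is also labelled a pilot, and at N=50 the problems are moderate.

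Four stronger readings are tempting and not supported:
- That the plan fits a ten-slope model to a primary outcome. No such model is named for week-8 granulation.
- That false positives multiply. Likelihood-ratio tests would over-reject (14/15/18% at N=34, 9/9/12% at N=50), but G2 does not name that test, and Wald tests stay near or below nominal.
- That the decision on a further trial would be distorted. G1 does not say which statistic defines a trend, so this is possible and not shown.
- That adjustment itself is wrong. The problem is many covariates combined with unpenalised estimation.

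On mobility, a baseline questionnaire could supply the measure ("To evaluate functional status we will use well-accepted questionnaires, SF-12 for Quality of Life"), and the visit table that F2 refers to is not in the text available. The point is only that the plan should say which measure it means.

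**Conclusion.** The concern holds in conditional form. The established defect is a nine-variable adjustment rule with no model attached, beside planned logistic comparisons of arms in 34 or 50 patients. If the rule is applied to those comparisons by ordinary maximum likelihood, a true odds ratio of 2.7 is typically reported as about 4–5 (N=34) or 3.6–3.9 (N=50). With no effect, neither product is favoured on average, but at N=50 threefold apparent differences are about twice as frequent as with two covariates.

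The events-per-slope ceilings need only N and the number of slopes. The other sizes rest on the assumed success rates, covariate effects and independence. Dropout was not modelled; losing patients would make matters worse. The count and hazard-ratio models were not examined. This should be corrected, cheaply, before outcomes are compared by arm; it does not invalidate the trial.

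**What to change.** Replace the adjustment sentence in G2 with text to this effect:

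> Treatment comparisons of binary outcomes (granulation at week 8, healing at weeks 12 and 16) will be adjusted for baseline wound area and at most one further pre-treatment covariate, named before any outcome is compared by arm. The unadjusted comparison will be reported alongside. The other listed variables will be used only in the exploratory one-at-a-time predictor analysis.

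If the team prefers to keep all nine, state instead that these comparisons will use Firth penalised logistic regression. One of the two changes is enough. The choice of test, interval and method for missing covariates is optional, provided that it is stated. Leave mobility status out of the treatment-adjustment set unless it is a defined pre-treatment measure.

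Costs:
- Chance imbalance in dropped covariates is described and not adjusted for.
- If the dropped covariates are prognostic, the odds ratio is somewhat attenuated: 2.3–2.5 for a true 2.7 with two-covariate Firth.
- There is little or no power gain at N=50: Wald power is 37/30/18% with nine covariates and 36/31/18% with two. At N=34 it is 16/10/3% against 26/20/10%.
- Firth with all nine costs some power: 32/27/19% at N=50, against 36/31/23% for Firth with two.

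The change is mainly wording, with one procedural check. F2 puts the baseline assessments and the application on the same day without giving their order: "Matrix application, Upper Extremity Test, Peripheral Neuropathy, Thermal Image, Vascular Assessment, Wound Assessment, Wifi Wound Classification, and Wound photo". The plan should confirm that the chosen covariates are recorded before the matrix is applied.

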#### Inclusion Criteria:

\*Type II Diabetes or Peripheral Artery disease \*Non-infected deep wounds (Grade 2 in the Wagner Ulcer classification) \*18 years or older

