Device Acceptability Questionnaire: The subject will be handed a questionnaire to evaluate the study device and provide feedback to the research team. We will be asking about level of satisfaction with the product. These may be questions about the time spent to apply the product, the level of comfort, appearance of the product, the appearance of the healed wound (e.g. presence of scarring), ease of walking or standing with the product and after healing, etc.

Matrix Application: During the subject's wound treatment (either in OR or outpatient clinic), the physician will apply the dermal matrix from the group they were placed. The researchers will write down the duration needed for full application of the product. For accurate estimation of time needed for preparation and application, the whole process may be video-recorded for offline estimate of each time.

Vascular Assessment: We will assess perfusion of the macro-circulation with arterial Doppler studies and micro-circulation with Skin Perfusion Pressure measurements. Ankle Brachial Index (ABI) will be measured on both extremities. We will also use the SensiLase system (Väsamed) to measure Skin Perfusion Pressure (SPP) in mmHg. Additionally, we may use the LUNA or SPY Device for Indocyanine Green Fluorescence Imaging. For this purpose a fluorescent agent may be injected into the subject's body to allow us observe the blood circulation to the wound. Indocyanine Green Fluorescence Imaging (SPY or Luna) may be performed based on the medical judgment of the physician. Highly qualified medical/clinical staff will perform this measurement. If so, measurement will take place only during baseline and treatment day.

Wound Photo: At every visit, the Medical/Researcher using a standard digital camera will take a digital photo of the wound. We will ask the subject's permission to take photos/video.

Wound Assessment: Evaluations will be based on data collected from wound assessments and photographs. We use acetate tracings and digital photos. Additionally, we will use thermal imaging to track inflammation.

Thermal Image: A thermal camera will be used to obtain an image of the wound and observe swelling.

Wifi Wound Classification: Podiatrist or vascular surgeon will evaluate the health and wellness of the subject's feet in compliance of standard of care

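### The plan promises control for initial wound size but takes the percent-wound-area p-values from t tests, which cannot carry that covariate

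*Combined protocol and SAP*

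**What the plan says.** Three sentences in section G2 (Data Analysis) bear on the wound-area data.

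- Secondary outcomes in general: "Appropriate mixed models (linear or generalized linear, for noncontinuous outcomes or logistic regression for binary data) will be used to test the intervention effect". Section F1 lists as secondary the "weekly speed of wound healing after successful granulation and transition to standard wound therapy".
- Covariates, straight after the univariate logistic regressions: "Results will be controlled for potential confounding variables including age, sex, BMI, HbA1c, neuropathy severity, vascular status, frailty, mobility status, and initial wound size". The analyses that this covers are not stated.
- The next sentence: "The p-values for weekly % wound area and % wound area reduction through 16 weeks will be calculated using t tests". No covariate is named, and the denominator of the percentage is not defined, though it is presumably the patient's own baseline area.

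Baseline area will be available. The Screening/Baseline visit in section F2 includes "Vascular Assessment, Wound Assessment, Wifi Wound Classification, and Wound photo", and F2 says of wound assessment: "We use acetate tracings and digital photos".

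The eligibility criteria fix the Wagner grade but set no lower or upper limit on wound area. Section F1 describes randomization into two groups and mentions no stratification.

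**The concern.** If initial wound size predicts percent area, as its place on the confounder list implies that it may, a t test leaves that variation in the error term. It also leaves any chance difference in starting size in the product comparison. Dividing by baseline area removes the dependence only if the percentage is unrelated to starting size.

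The stakes are in interpretation. Section D gives weekly change in wound size as its first example of the wound outcomes to be compared. Section G1 would use trends seen in this study to support a further trial or a larger sample. With 17 per group, or 25 if the total of 50 in G1 applies, one unlucky randomization could colour such a trend. Two statisticians reading G2 could also reasonably run different analyses and report different p-values.

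**Working it through.** **1. The plan's own figure.** G1 uses application times of 3 v. 5 min with SD 2, so d = (5−3)/2 = 1, with two-sided alpha 0.05 and power 80%. The noncentral t solution is 16.71 per group, rounded up to 17, as stated. Power at 17 per group is 80.7%. The calculation concerns application time; the documents give no effect size or power for wound area. Below, d=1 is only a benchmark.

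**2. Power with baseline area in the model.** The noncentrality is

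d × √(n/2) / [√(1−r²) × √(1 + 1/(2n−4))], on 2n−3 degrees of freedom.

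The factor 1 + 1/(2n−4) is the average penalty for covariate imbalance; at n=17 it is 1 + 1/30. For r=0.4: √(17/2) = 2.915; √(1−0.16) = 0.917; √(1+1/30) = 1.017; noncentrality 3.13 on 31 df; power 85.8%.

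| r (assumed) | Power with baseline area, n=17, d=1 | Change from 80.7% |
|---|---|---|
| 0 | 79.3% | −1.4 points |
| 0.2 | 80.9% | +0.2 |
| 0.3 | 83.0% | +2.3 |
| 0.4 | 85.8% | +5.1 |
| 0.5 | 89.4% | +8.7 |

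At 25 per arm, with the effect set so that the t test has 80% power (d=0.81), the adjusted model has 79.1% at r=0, 82.7% at r=0.3 and 89.2% at r=0.5. The pattern is the same.

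**3. Chance imbalance.** The difference in mean baseline area between arms, in SD units, has standard error √(2/n). At n=17, 0.5/√(2/17) = 1.458, so the probability of an imbalance above 0.5 SD in either direction is 14.5%. At n=25, 0.5/√(2/25) = 1.768, giving 7.7%.

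**4. False positives of the t test with no product effect** (simulation, 40,000 trials per setting, bivariate normal baseline and outcome):

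| | All trials | Trials with imbalance above 0.5 SD |
|---|---|---|
| n=17, r=0.3 | 5.0% | 8.1% |
| n=17, r=0.5 | 5.0% | 12.3% |
| n=25, r=0.3 | 5.1% | 8.3% |
| n=25, r=0.5 | 5.0% | 15.6% |

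**The case against.** **The plan already adjusts.** The covariate sentence names initial wound size, and mixed models are assigned to the secondary outcomes. A reader might infer from the t-test sentence that the plan makes no adjustment for baseline size at all. The documents do not support that: the scope of the covariate sentence is open, and it may be meant to reach these outcomes. But if it does, the named test cannot deliver it, and the t-test sentence is the only one that assigns a test to the percent-area p-values. What remains is an inconsistency, and it needs resolving on either reading.

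**A percentage already uses baseline.** This stands in part. Scaling by baseline may leave only a weak residual correlation, in which case adjustment gains nothing or costs a point or so. The documents cannot settle this, so a flat statement that power is lost would go too far.

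**The t test is valid.** A reader might infer that wound-size imbalance inflates the trial's false-positive rate. It does not: averaged over randomizations the rate is about 5%. The problem is confined to trials in which an imbalance has occurred.

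**It matters little here.** Percent area is not one of the three primary outcomes in F1 and G2, the wound outcomes in section D are assumed comparable, and F1 classes the study as a pilot. This stands, and it limits the weight of the point.

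**Conclusion.** The point holds as an internal inconsistency in G2: control for initial wound size is promised, and the next sentence names a test that cannot provide it. Removing the inconsistency in favour of a baseline-adjusted model would add about 2 points of power at r=0.3, 5 at r=0.4 and 9 at r=0.5. It adds essentially nothing at r=0.2 and costs 1 to 2 points if r is near 0. It would also protect the comparison in the roughly one trial in seven (17 per arm) with a baseline imbalance above 0.5 SD.

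These figures rest on an assumed range for r, on d=1 borrowed from application time, and on approximately normal data. Importance is modest, but the correction is cheap and worth making before any data are compared.

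**What to change.** Replace the t-test sentence in G2 with:

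> Percent wound area and percent area reduction through week 16 will be compared between arms by a linear model (or one repeated-measures mixed model across weeks) with terms for arm and log baseline wound area; a rank-based analysis of covariance is the sensitivity analysis.

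State also that the percentages are relative to baseline area, if that is meant, and which analyses the covariate sentence covers.

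A model for log(area + constant) may look attractive but should not be the replacement. Healing is a planned outcome at 12 and 16 weeks, and closed wounds become extreme values on that scale, placed by an arbitrary constant. An illustrative simulation used 17 per arm, log-normal areas with log baseline SD 1.0, slope 0.3 of log ratio on log baseline, residual SD 0.6 and arm effect −0.7, all assumed. With few closures, power was 77% for the t test and 89% for the log model. With 20% of wounds closed in each arm, it was 47% for the t test, 50% for percent area with log baseline added, and 17% for the log model (constant 0.05).

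The cost is one sentence and one degree of freedom, with no new data or visits. The downside is the small power loss if percent area turns out to be unrelated to baseline area.
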